3.2.2. Pharmacokinetic profile

Another secondary objective is to characterize the PK profile of orally administered VH4524184. The estimand is described by the following attributes:

- **Population:**
Overtly healthy (other than HIV-1 infection) treatment naïve individuals
- **Endpoints: as data permits**
 - Maximum observed plasma drug concentration (Cmax)
 - Time to maximum observed plasma drug concentration (tmax)
 - Concentration on Day 10
- **Treatment:**
VH4524184 or placebo **CCI** followed by SOC on Days 10-38
- **Intercurrent events:**
 - Discontinuation of study treatment due to any reason will be addressed using **while on-treatment strategy**, i.e. PK data after study treatment discontinuation will be excluded from use in noncompartmental analyses.
 - Use of SOC medication prior to Day 10 will be addressed using **while on-treatment strategy**, i.e., PK data collected after initiation of SOC, if for any reason this takes place prior to Day 10, will be excluded
 - Use of prohibited medication will be addressed using **treatment policy strategy**, i.e., all PK data will be used regardless of the use of prohibited medication
 - **CCI** of study treatment will be addressed using **while on-treatment strategy**, i.e., PK data collected **CCI** will be excluded from use in noncompartmental analyses.
- **Population-level summary:**
Summary statistics (e.g. arithmetic mean, SD, median, min, max, geometric mean, SD (log), %CVb, etc.)

Rationale for estimand: Interest lies in characterizing the PK profile of orally administered VH4524184 which could be biased by study treatment discontinuation, **CCI**, or use of SOC medication prior to day 10.

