4. STUDY DESIGN

4.1. Overall design

This is a Phase 2a POC, multi-center, randomized, double-blind (sponsor unblinded), placebo-controlled, adaptive clinical study to evaluate the antiviral effect, safety, tolerability and PK/PD of orally administered VH4524184 over 10 days in up to approximately 28 ART naïve adults with HIV-1 and detectable viremia.

This study will be conducted in 2 parts. In Part 1, 21 TN participants will be randomized to 1 of 3 cohorts. Within each cohort, 6 participants will receive VH4524184 and 1 will receive matching placebo **CCI**

Part 2 of the study is optional. The conduct of Part 2 is dependent on the informal interim evaluation of the exposure-antiviral response data from Part 1 using available preliminary clinical data from Part 1. Interim analysis of Part 1 will determine if evaluation of a fourth dose of VH4524184 would be informative to properly characterize the exposure-antiviral relationship. If evaluation of a fourth dose is needed, Part 2 will be conducted and will include 1 additional cohort in which up to 6 participants would receive VH4524184 and 1 would receive matching placebo. Part 2 may evaluate 1 additional dose, with the dose and frequency informed by PK/PD modelling of Part 1 data.

In both Part 1 and Part 2, each dose of VH4524184 will be evaluated as double-blind (Sponsor unblinded) monotherapy for 10 days (primary endpoint). On Day 10, participants will start open-label SOC ART that is selected by the investigator and locally sourced. Participants will be followed weekly through Day 38. **CCI**

[REDACTED]

[REDACTED]

All participants will be screened for eligibility preferably within approximately 7 to 14 days before being randomized into a 10-day study intervention period. The screening period may be extended to 28 days to allow, at a minimum, receipt of all screening results and/or to accommodate scheduling.

Following screening, the study requires a total of 9 in-clinic visits (5 in-clinic visits will occur in the Monotherapy Period; 4 in-clinic visits will occur in the Open Label Follow-up Period) and 3 virtual visits (3 virtual visits will occur in the Monotherapy Period; participant may choose to attend the visit in clinic and this is acceptable). **CCI**

[REDACTED]

[REDACTED]

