3. ANALYSIS SETS

Analysis Set	Definition / Criteria	Analyses Evaluated
Screened	
 • All participants who were screened for eligibility 	
 • Study Population
Randomized	
 • All participants who were randomly assigned to study intervention in the study. 	
 • Study Population

Analysis Set	Definition / Criteria	Analyses Evaluated
Safety	
 • All randomized participants who received at least 1 partial or full dose of study intervention. • Participants will be analyzed according to the study intervention they actually received 	
 • Study Population • Safety
Full Analysis Set (FAS)	
 • All randomized participants who received at least 1 full dose of study intervention. • Data will be reported according to the randomized study intervention. 	
 • Study Population • Efficacy
Per-Protocol (PP)	
 • All participants in the FAS for whom there were no major protocol deviations that impact the primary analyses. • Data will be reported according to the study intervention actually received. • Specific details of major protocol deviations that would exclude participants from the PP analysis set are provided in Section 3.1. 	
 • Efficacy • The PP set will not be used for analysis if it is the same as FAS
Pharmacokinetic (PK)	
 • All participants in the Safety analysis set who had at least 1 non-missing PK assessment (Non-quantifiable [NQ] values will be considered as non-missing values). • Data will be reported according to the actual study intervention. 	
 • PK

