3.1. Exclusions from the Per Protocol Analysis Set

A participant meeting any of the following criteria prior to the end of monotherapy period will be excluded from the primary analysis based on the PP analysis set:

Number	Exclusion Description
01	Missed at least one dose or received a partial dose
02	Took at least one incorrect dose
03	Missed the Day 1 or Day 10 HIV-1 RNA assessment
04	Missed more than 1 post-baseline HIV-1 RNA assessment between Day 1 and Day 10
05	Started the SoC medication prior to Day 10
06	CCI
07	Violated any of the inclusion criteria or met any of the exclusion criteria

Number	Exclusion Description
08	Met other Important Protocol Deviations occurring during the monotherapy period meriting exclusion from the PP analysis set as they have the potential to significantly impact primary analysis. Protocol deviations will be adjudicated throughout the study conduct and will be classified as important (yes/no), along with determination on whether they should trigger exclusion from the PP analysis set and finalised prior to DBL.

*Medical monitor and PK lead will review the list of prior and concomitant medications used by participants in the study and determine which ones meet the criteria of strong/moderate inducers/inhibitors described here prior to DBL.

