4.2.3. Sensitivity analyses

The primary analysis described in section 4.2.2 will be repeated on the PP analysis set, and on the Safety analysis set if any participant receives treatment other than the one to which they were randomized.

None of the IEs specified in section 1.1 for the primary estimand are applicable for the PP analysis set, as none of them can occur in participants within the PP analysis set (because of criteria in section 3.1). All available HIV-1 RNA data from the monotherapy period on the PP analysis set will be used for the sensitivity analysis.

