PK concentrations derived after discontinuation of study treatment will be excluded from PK data summaries, in accordance with the 'while on-treatment' strategy for IE, as described in section 1.1.

If a participant takes an incorrect dose or misses a dose, PK concentrations and PK parameters inferred until the next dose or until the end of monotherapy period (if incorrect dose is the last one) may be excluded from PK data summaries, as instructed by CPMS prior to final database lock.

The following figures will be produced:

- A by-subject graph of the concentration data over time, on linear and semi-logarithmic scales
- Graph of geometric mean of concentration data over time, on linear and semi-logarithmic scales
- Individual and box plot of PK parameters

Listings of PK concentration and PK parameter values will be produced.

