4.6.2. Other pharmacokinetic analyses

All other pharmacokinetic analyses will be performed on the Pharmacokinetic analysis set and will follow the IE strategies outlined for the secondary PK objective in section 1.1.

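### The plan keeps all PK data after prohibited medication and has no supplementary PK summary without samples affected by a strong or moderate inducer or inhibitor, although such drugs are to be identified for the antiviral Per Protocol set.

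*Protocol*

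**What the plan says.** Protocol 3.2.2 and the PK estimand in SAP 1.1 apply the same rule to prohibited medication: "all PK data will be used regardless of the use of prohibited medication". The same estimand drops PK data after treatment discontinuation and after early standard-of-care ART. Its rationale begins: "Interest lies in characterizing the PK profile of orally administered VH4524184 which could be biased by study treatment discontinuation". It goes on to a redacted item and early standard-of-care use. Prohibited medication is not among the visible items.

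SAP 3.1 lists the Per Protocol exclusions. Criterion 06 is redacted, but the footnote has the medical monitor and PK lead review medications and "determine which ones meet the criteria of strong/moderate inducers/inhibitors described here prior to DBL". SAP 3 assigns the Per Protocol set to efficacy only, and SAP 4.2.3 describes its use: "All available HIV-1 RNA data from the monotherapy period on the PP analysis set will be used for the sensitivity analysis".

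The PK set is "All participants in the Safety analysis set who had at least 1 non-missing PK assessment". SAP 4.1.1 and 4.3.2.3 remove out-of-window samples from PK summaries, and 4.3.2.3 also removes samples after discontinuation. After an incorrect or missed dose, values "may be excluded from PK data summaries, as instructed by CPMS prior to final database lock". Nothing similar covers an interacting drug. Under SAP 4.6.2 the other PK analyses "will follow the IE strategies outlined for the secondary PK objective in section 1.1".

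**The concern.** Inducers and inhibitors act first on exposure and reach viral load only through it. The plan screens for them where the effect is indirect (HIV-1 RNA) and not where it is direct (PK concentrations and parameters). The estimand sets out to describe the PK profile free of certain biases, yet a sample taken outside its window leaves the summary while one taken under a strong inducer stays in.

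The arms are small: "Within each cohort, 6 participants will receive VH4524184 and 1 will receive matching placebo". One affected participant is a sixth of an arm. At stake are the Cmax, AUC and Day 10 concentration summaries for that dose, the reported between-participant variability and, if they are run, the dose-proportionality slope and the accumulation ratio.

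**Working it through.** The plan states no PK precision figure to reproduce. The sample size is feasibility-based and the precision table is redacted.

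**Inputs from the documents.** 6 active participants per cohort and 3 cohorts in Part 1 (Protocol 4.1); a power model on the log scale with a 90% CI, and proportionality assumed if the CI contains 1 (SAP 4.6.2.1).

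**Assumptions, not in the documents.** One participant's exposure is multiplied by f = 2, 3 or 0.3; underlying geometric CV is 25% for the arm summary and 30% for the slope; three equally log-spaced doses span 10-fold.

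**Geometric mean.** Ratio = f^(1/6).
- f = 2: 1.122, or +12%
- f = 3: 1.201, or +20%
- f = 0.3: 0.818, or -18%

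The accumulation ratio moves by the same factor if the interaction is present at the last dose and absent on Day 1, and all six have both values.

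**Geometric CV.** Shifting one of six log values by ln f adds (ln f)²/6 to the expected log variance. The starting value is ln(1 + 0.25²) = 0.0606, and CV = √(exp(variance) - 1).
- f = 2: 0.0606 + 0.0801 = 0.1407, CV 39%
- f = 3: 0.0606 + 0.2012 = 0.2618, CV 55%
- f = 0.3: 0.0606 + 0.2416 = 0.3022, CV 59%

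**Power-model slope.** The centred log doses are -L, 0 and +L, with L = ln(10)/2 = 1.151. Sxx = 12L² = 15.9. A top-cohort participant shifts the slope by L·ln f/Sxx.
- f = 3: 1.151 × 1.099/15.9 = 0.080
- In the bottom cohort the sign reverses.
- In the middle cohort the shift is 0 and only the CI widens.

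With no affected participant the standard error is √ln(1.09)/√15.9 = 0.294/3.99 = 0.074. Simulating the top-cohort case raises the mean estimated standard error to 0.096, so the shift is about 0.8 of it. With a true slope of 1 the 90% CI then contains 1 in about 87% of trials, against 90% nominal. In the middle cohort the mean CI width goes from 0.25 to 0.34 and the CI contains 1 in about 97%.

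A wider CI makes proportionality easier to accept. In a deliberately harsh case (true slope 0.75, 2-fold dose steps, 30% CV), it is accepted in 38% of simulated trials with nobody affected, 98% with f = 5 in the top cohort and 78% with f = 0.2 in the middle cohort.

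**Cost of leaving one out.** The half-width of a 95% interval on the log mean is t/√n in SD units: 2.776/√5 = 1.241 against 2.571/√6 = 1.049, or about 18% wider.

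**The case against.** **Treatment policy is a declared choice.** The antiviral, safety and PK estimands all treat prohibited medication this way, and the protocol and SAP agree. A reader might infer that the documents contradict themselves. They do not. This stands, and it is why the estimand need not change.

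**The event may never happen.** Exclusions 13 and 16 (Protocol 5.2.2), the limits on co-medication in Protocol 2.3.1, 6.9 and 6.9.1, and medication review at each monotherapy visit all make it less likely over a 10-day period. This stands. The documents give no probability, and the point is conditional. But the sponsor wrote a rule for the event, so its consequence is worth settling.

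**The link is inferred.** Criterion 06 and the prohibited list are redacted, and Protocol 6.9.2 points to 5.2.2, which covers more than inducers and inhibitors. The support is the SAP 3.1 footnote, plus the statement in SAP 4.2.3 that none of the primary estimand's intercurrent events, which include prohibited medication, can occur in the Per Protocol set.

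**An outlier would be seen.** Medians, ranges, by-subject plots and PK and medication listings are planned. This stands, but seeing an outlier is not a rule for handling it, and an exclusion decided afterwards in an arm of six would be open to challenge.

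**Exposure-response and Part 2.** A reader might infer that the rule distorts the exposure-antiviral relationship or the Part 2 dose. The documents do not show this. Those analyses relate PK parameters to RNA change, with covariates possible, under a separate clinical pharmacology plan (Protocol 9.3.3.3; SAP 4.3.2.4), and are not described as using cohort means. A participant's actual concentration belongs with that participant's actual response.

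**Conclusion.** The gap is real and modest. No planned PK summary, dose-proportionality analysis or accumulation analysis separates the study drug's own kinetics from an interaction, although the information to do so is already due before database lock. One affected participant in six would move an arm's geometric mean by roughly 10% to 20% and raise its reported CV by about half to more than double, under the assumed fold changes and the assumed 25% CV.

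The slope result is weaker. Dose proportionality is optional, the estimate is biased only from an outer cohort, and in the 3-fold case the shift is below one standard error as actually estimated. The harsh masking case depends on its extreme assumptions.

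Interaction size, PK variability and dose span are redacted or absent, so these figures are a range and not a forecast. They do not support replacing the estimand strategy or removing anyone from exposure-response. They support a cheap supplementary analysis.

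**What to change.** Keep the treatment-policy estimand in Protocol 3.2.2 and SAP 1.1. Add to SAP 4.3.2.3 a supplementary PK summary, and to SAP 4.6.2 a repeat of any dose-proportionality or accumulation analysis, that leaves out samples affected by a strong or moderate inducer or inhibitor, and parameters derived from them. Use the list already adjudicated for SAP 3.1, and record with it, before database lock, which samples count as affected. Produce these outputs only if such use occurs, and keep all values in the listings. Leave the exposure-response dataset unchanged.

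The cost is a few sentences in the SAP and one conditional table, plus the repeat of any SAP 4.6.2 analysis that is run. An arm may be summarised on 5 rather than 6, with the interval about 18% wider as shown. Because the list is due only before database lock, it may not be ready for the Part 1 interim analysis, so this change would not necessarily reach that look.

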4. STUDY DESIGN

4.1. Overall design

This is a Phase 2a POC, multi-center, randomized, double-blind (sponsor unblinded), placebo-controlled, adaptive clinical study to evaluate the antiviral effect, safety, tolerability and PK/PD of orally administered VH4524184 over 10 days in up to approximately 28 ART naïve adults with HIV-1 and detectable viremia.

This study will be conducted in 2 parts. In Part 1, 21 TN participants will be randomized to 1 of 3 cohorts. Within each cohort, 6 participants will receive VH4524184 and 1 will receive matching placebo **CCI**

Part 2 of the study is optional. The conduct of Part 2 is dependent on the informal interim evaluation of the exposure-antiviral response data from Part 1 using available preliminary clinical data from Part 1. Interim analysis of Part 1 will determine if evaluation of a fourth dose of VH4524184 would be informative to properly characterize the exposure-antiviral relationship. If evaluation of a fourth dose is needed, Part 2 will be conducted and will include 1 additional cohort in which up to 6 participants would receive VH4524184 and 1 would receive matching placebo. Part 2 may evaluate 1 additional dose, with the dose and frequency informed by PK/PD modelling of Part 1 data.

In both Part 1 and Part 2, each dose of VH4524184 will be evaluated as double-blind (Sponsor unblinded) monotherapy for 10 days (primary endpoint). On Day 10, participants will start open-label SOC ART that is selected by the investigator and locally sourced. Participants will be followed weekly through Day 38. **CCI**

[REDACTED]

[REDACTED]

All participants will be screened for eligibility preferably within approximately 7 to 14 days before being randomized into a 10-day study intervention period. The screening period may be extended to 28 days to allow, at a minimum, receipt of all screening results and/or to accommodate scheduling.

Following screening, the study requires a total of 9 in-clinic visits (5 in-clinic visits will occur in the Monotherapy Period; 4 in-clinic visits will occur in the Open Label Follow-up Period) and 3 virtual visits (3 virtual visits will occur in the Monotherapy Period; participant may choose to attend the visit in clinic and this is acceptable). **CCI**

[REDACTED]

[REDACTED]

If participants prematurely discontinue the study for non-safety reasons, additional participants may be recruited with randomization and assignment to the same cohort (to ensure a minimum of 5 evaluable participants in each of cohorts 1, 2 and 3, and optional cohort 4) at the discretion of the Sponsor in consultation with the Investigator. Participants will not be replaced if the reason for discontinuation is the original participant meeting stopping criteria.

Total duration of study participation is approximately 45 to 66 days based on the following:

- **Screening Period:** 7 to 14 days, with a maximum of 28 days permitted in some cases for screening/qualification period.
- **Monotherapy Period:** 10 days for treatment with the study intervention and assessment at all planned visits.
- **Open Label Follow-up Period:** 28 days for follow up visits while on SOC ART including the final follow up visit.

See Section 1.3 (Schedule of Activities) for additional details of activities during screening, the monotherapy period and the SOC period.

4.2. Scientific rationale for study design

This is a Phase 2a, multi-center, randomized, double-blind (sponsor unblinded), placebo-controlled, adaptive design, proof of concept clinical study to evaluate the antiviral effect, safety, tolerability, and PK/PD of 10 days of orally administered VH4524184 monotherapy, an investigational HIV-1 CCI [REDACTED], in ART naive HIV-1 viremic adults.

On Day 10, all participants will switch to standard-of-care antiretroviral therapy selected by the investigator CCI [REDACTED]
[REDACTED]
[REDACTED]

Though there are commercially available/approved CCI [REDACTED] available data suggests that CCI [REDACTED] resistance does not occur during short periods of CCI [REDACTED] monotherapy; therefore, dosing with VH4524184 will not interfere with selection of the ART regimen selected by the investigator on Day 10 and any subsequent regimen following completion of the study.

The purpose of this study is to evaluate the short-term safety and effect on reducing HIV-1 RNA levels from baseline for different doses of orally administered VH4524184. This study will facilitate an initial understanding of the antiviral activity and safety profile of VH4524184 in an HIV positive ARV naïve adult population, while limiting the monotherapy exposure to reduce the likelihood of development of viral resistance. The data gathered from this study, together with data from the 2 ongoing Phase 1 studies will inform subsequent clinical trials and Phase 2b clinical development CCI [REDACTED]
[REDACTED]
[REDACTED]

There is an established precedence to use a randomized placebo-controlled short-term monotherapy design in a small number of participants when initially evaluating the activity of new investigational HIV anti-viral agents. This design allows an early understanding of the anti-viral potency and emerging safety profile across different doses while limiting the duration of exposure to the fewest number of HIV-infected participants. The placebo control maintains the blind, reduces bias in the investigator's evaluation and management of safety events, and permits a comparison of safety and efficacy outcomes between the investigational product and placebo.

The 2-part adaptive design will allow for interim evaluation of the exposure-antiviral response data to determine if evaluation of a fourth dose of VH4524184 would be informative to properly characterize the exposure-antiviral relationship. If a fourth dose is not needed, then exposing additional participants to the investigational product can be avoided.

4.2.1. Participant input into design

[figure not shown]
Community advisors living with HIV were engaged in development of this short-term monotherapy proof-of-concept study design. The group of highly experienced patient advocates provided feedback on protocol feasibility and informed guidance for study implementation (such as considerations for assessment of site facilities, potential services to ease participant burden during longer visits and travel to site, potential inclusion of POCBP in the study population, and considerations for the development of the informed consent document).

4.3. Justification for dose

The pharmacokinetics following CCI [REDACTED] VH4524184 has been characterized in study 218803 [IB, 2023]. The CCI [REDACTED] cohort in 218803 CCI [REDACTED]. Exposures in the highest dosing cohort in this study will be lower than what has been observed in 218803 and based on the tolerability and safety profile in the FTiH CCI study, dosing in the PoC protocol is considered safe. A POP PK model was developed from participant VH4524184 PK observations collected in study 218803. CCI [REDACTED]

[REDACTED]. Details for POP PK model development are described in the 218804 Human Dose Prediction Report [GSK Study report TMF-16733560]. The POP PK model is being leveraged herein to simulate VH4524184 exposures that achieve desired trough concentrations across 3 dosing Cohorts. The in vitro target trough concentration for VH4524184 is CCI [REDACTED] [REDACTED]. Doses of CCI [REDACTED] were selected for this study to establish an in vivo dose-response relationship by targeting typical subject trough concentrations that CCI [REDACTED]

Figure 2 Simulated Plasma concentrations of VH4524184 Achieved Following Dosing of CCI [REDACTED]

The maximum reduction of HIV-1 RNA from baseline ($\sim 2 - 2.5$ log₁₀ reduction) has been consistent across CCI [Markowitz, 2006; Min, 2011; Spreen, 2013; Gallant, 2017]. CCI of VH4524184 CCI is anticipated to achieve maximum Day 10 reduction of HIV-1 RNA from baseline for all participants. Depending on the virologic response observed in the three planned cohorts, an additional cohort may be enrolled to further describe the relationship between VH4524184 exposure and HIV-1 RNA levels. In this instance, PK/PD modeling will be used to inform the dose and frequency of the optional Part 2 cohort.

